## SECTION 1: STUDY SUMMARY

American Indian (AI) communities in the United States (US) are disproportionately affected by sexual and reproductive health disparities, compared to other populations, placing current and future generations of AI societies in jeopardy. Our study, "Nen OnkUmbi/EdaHiYedo (*NIE* - "We are Here Now")", utilizes a culturally tailored ecological intervention in which the prevention of sexual-risk behaviors among AI youth that lead to STIs, HIV, HCV, and teen pregnancy are addressed. *N/E* takes place on the Fort Peck Reservation in northeastern Montana. *N/E* is a community-based participatory research sexual and reproductive health (SRH) intervention, constructed on Ecological Systems Theory. Based on Fort Peck tribal members' desire to implement a holistic SRH intervention for the tribes' youth, *N/E* includes: 1) A school-based SRH curriculum called Native Stand, designed to address individual-level factors that lead to risky behaviors; 2) a family-level curriculum called Native Voices, tailored to increase communication between adult family members and youth about SRH topics; 3) a cultural mentoring component at the community-level that pairs AI youth with adults and elders to discuss traditional AI beliefs and practices about SRH; and 4) a systems-level strategy to activate a multi-sectoral network of local youth servicing organizations to coordinate SRH services. The overarching aim of this proposal is to refine and tailor the components of *N/E* and evaluate its efficacy. *N/E* is a 5-year study involving 456 15- to 18-year-old AI youth and their parent/legal guardian.

## 2.3 RESEARCH DESIGN OVERVIEW

**2.3.1 Study Title.** Nenunkumbi/Edahiyedo ("We Are Here Now"): A Mult-level, Multi-component Sexual and Reproductive Health Intervention for American Indian Youth

**2.3.2 Study Aims.**

- **AIM 1** begins with a year of formative work to refine and tailor the components of N/E. Our community advisory board and the Fort Peck-based and MSU-based research team will design culturally appropriate adaptations for N/E's 4 levels.
- **AIM 2** tests the efficacy of N/E using a cluster-randomized stepped-wedge design (SWD), in which the 5 high schools that Fort Peck youth attend are randomized into the intervention 1 at a time. N/E's primary outcome is increased condom use during sexual intercourse. Secondary outcomes are delayed onset of sexual intercourse, number of sex partners, frequency of sexual intercourse, pregnancy history, consistent use of birth control during sexual intercourse, and whether alcohol and/or other drugs are used during sexual intercourse. Tertiary outcomes are increased parent/legal guardian-child communication about SRH topics, increased understanding of cultural values related to traditional AI beliefs regarding SRH, and increased use of SRH services. Quantitative data collection includes: student surveys at baseline, 3, 9 and 12 months; parent/legal guardian surveys at baseline, 9 and 12 months. Qualitative data collection includes SRH service provider discussion groups at baseline and thereafter once a year over the 5-year study, with logs to track coordination and implementation at baseline and 3, 6, 9 and 12 months.
- **AIM 3** will evaluate the fidelity and acceptability of N/E with focus groups, activity logs, and staff meeting notes and staff field notes.

Our **long-term goal** is to produce a toolkit, including curriculum manuals, an SRH cultural mentoring program, and specific systems-level actions suitable for replication in other tribal communities. The **public health impact** is the prevention of STIs, HIV, HCV, and teen pregnancies in AI youth resulting in reduced sexual and reproductive health disparities and improved health in AI families and communities.

**2.3.3 Design Overview.** *NIE* is a community-based participatory research (CBPR) multi-level, multi-component sexual and reproductive health (SRH) intervention, constructed on Ecological Systems Theory. *NIE* is based on Fort Peck tribal members' desire to implement a holistic SRH intervention for AI youth. *NIE* includes: 1) A school-based SRH curriculum called *Native Stand*, designed to address **individual-level** factors that lead to sexual risk behaviors; 2) a **family-level** curriculum called *Native Voices*, tailored to increase communication between adult family members and youth about SRH topics; 3) a cultural mentoring component at the **community level** that pairs AI youth with adults and elders to discuss traditional AI beliefs and practices about SRH; and 4) a mobilizing strategy to activate a multi-sectoral network of youth-servicing organizations at the **systems level** in Fort Peck to coordinate SRH services for AI youth. The overarching aim of this study is to refine, tailor, and finalize the components of *NIE* and evaluate its efficacy. We will use a cluster-randomized stepped-wedge design (SWD), in which 5 schools that AI youth from Fort Peck attend are the clusters to be randomized into the intervention 1 at a time, with all schools eventually being randomized to the intervention. The 5 schools are located in separate communities, mitigating the potential for cross-contamination. *NIE* is a 5-year study involving 456 15- to 18-year-old AI youth.

**2.3.4 Intervention Design.** *NIE* is a 5-year CBPR ecological intervention for 456 15- to 18-year-old AI youth living on the Fort Peck Reservation. *Nen OnkUmbilEdaHiYedo* ("We Are Here Now") derives from the Assiniboine (*Nen OnkUmbt*) and Sioux (*EdaHiYedo*) names for their traditional coming-of-age ceremonies, when, at the age of 15 and over, young tribal members are believed to be ready for integrated education and training on sex, what it means to be a man or a woman, relationships, having children, and being a parent. *NIE* is guided by a 5-member CAB. The primary institutional partners responsible for the implementation of *NIE* are Fort Peck Community College (FPCC), the Fort Peck Tribes Language and Culture Program, the Fort Peck Tribal Health Department (Epi Team), and MSU.

*NIE* will be implemented simultaneously over the 9-month school year (Table 1). Components include: 1) **Individual Level.** *Native Stand* is a school-based, 27-module STI-, HIV-, and teen pregnancy-prevention curriculum, originally developed for rural white youth and adapted in 2008 as a stand-alone SRH curriculum for AI youth. For *NIE*, an adaptation of *Native Stand* will be implemented in the study's 5 high schools to educate AI youth on sexual risk behavior prevention strategies. The tailoring of *Native Stand* will reduce its 27 modules to 18 modules and will include specific community-relevant traditional and contemporary cultural lesson plans. *Native Stand* will be integrated into each of the 5 schools' established curriculum and will be delivered by the *NIE* School Coordinator in a classroom setting as part of the students' regular class schedule. 2) **Family Level.** *Native Voices* is a video-based HIV/STI-prevention intervention designed for AI youth to address condom use, negotiation skills, group discussion, and role playing. *Native Voices* will be adapted from 1 module into 4 modules to involve parents/legal guardians, as recommended by the CDC. Our adaptation of *Native Voices* involves students with one of their parents/legal guardians to promote parent/legal guardian/youth discussions about preventing STIs, HIV, HCV, and teen pregnancy. The *NIE* School Coordinator will present *Native Voices* to groups of students and their parents/legal guardians at the study's high schools for 2 hours in the evening. 3) **Community Level.** The third level of *NIE* is a cultural mentoring component that pairs AI youth with older adults and elders to discuss traditional AI beliefs and practices about reproductive health. The mentoring program is based on Assiniboine and Sioux traditional knowledge and the National Mentoring Partnership standards for mentoring. The mentoring program was designed specifically for Fort Peck youth by the Fort Peck Tribes' Language and Culture Department and has been in existence for 5 years. *NIE* integrates this cultural mentoring program into *NIE*'s overall framework with an emphasis on addressing traditional topics related to SRH, such as overall information on cultural beliefs, values, and ceremonies, and more specific information on cultural beliefs and values regarding sex, having children, parenting, and relationships. Our cultural mentoring program will include older male and female tribal members who will be paired with the youth by gender and tribal affiliation. AI youth will meet one-on-one with their mentors each month and also monthly in mentor-mentee small groups. Depending on the purpose of the cultural mentoring sessions, the sessions will take place at either the study's high schools, the Fort Peck Language and Culture Department's main office in Poplar, community centers on the reservation, or at the Buffalo Ranch. [name] will oversee the implementation of the cultural mentoring program. 4) **Systems Level.** The fourth level of *NIE* mobilizes the existing Epi Team to enhance the coordination and implementation of SRH services at Fort Peck. The members of the Epi Team will utilize the recommendations in the CDC's *Contraceptive and Reproductive Health Services for Teens: Evidence-based Clinical Best Practices Guide* to enhance the coordination and implementation of SRH services for AI youth. This enhancement process will take place during the Epi Team's monthly meetings at the Fort Peck Tribal Headquarters in Poplar by developing a coordination and monitoring plan that can be tracked over time to address the barriers, facilitators, and solutions to increase access to SRH

---

 Fort Peck Tribal Epidemiology Team (Epi Team), which is a local committee that has been in existence for 15 years to monitor diseases on the reservation and the health status of tribal members. The Epi Team is comprised of the Fort Peck Tribal Health Department; the Indian Health Service (Poplar Service Unit and Wolf Point Service Unit); the Roosevelt County Health Department; school nurses from the Fort Peck Health Promotion and Disease Prevention Program; the high schools of Frazer, Wolf Point, Poplar, Brockton, and Culbertson; and the Fort Peck Tribal Executive Board.

services for AI youth at Fort Peck. [name], [name], [name] and [name] will attend the Epi Team's monthly meetings to work in partnership to implement *NIE*'s systems-level component.

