**For the student and parent/legal guardian participating in *NIE*, there are 2 forms of data collection:** a student survey and a parent/legal guardian survey. [name], a part-time assistant, and the N/E school outreach coordinator will oversee both surveys' administration. The student surveys and parent/legal guardian surveys will be completed using Research Electronic Data Capture or "REDCap." REDCap is a secure web application for building and managing surveys and databases.

The students and parents will take the survey on iPads that have the mobile application version of REDCap installed on the tablets. The mobile app version of REDCap collects data offline to be uploaded to an online, secure database once a secure wifi location is reached. Deidentified data will be stored virtually on the REDCap server and available for download to [name], [name], [name], [name] and [name]. Only [name], the *NIE* outreach coordinator, and [name] will have access to names linking students and parents to their records during data collection and intervention implementation. These files will be kept in a locked file cabinet by [name] at MSU after data collection.

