From Years 2-4, 456 students and one of their parents/legal guardians will participate in *NIE*'s data collection. Student surveys for baseline, 3, and 9 months will be administered during regularly scheduled classes in an assigned classroom by [name], the assistant, and N/E's outreach coordinator. Baseline data collection will begin in March 2019 for all schools and parents included in the intervention. Groups of 20 students at a time will be appropriately spaced in the classroom in order to ensure privacy, and survey instructions will be presented to students prior to REDCap administration. [name], the assistant, and the *NIE* outreach coordinator will thoroughly review the assent form with the students, which will include a description of *NIE*, types of questions that will be asked, and potential risks and benefits of participating in *NIE*. All students will be reminded that they can withdraw at any time without consequences. Prior similar procedures have been successfully used by [name] and [name] for data collection in the Fort Peck schools with AI youth. For students who graduate from high school prior to the 12-month follow-up, they and their parent/legal guardian will be contacted by [name] to complete the 12-month follow-up (during evening hours) at the high school from which they graduated following the same procedure described above. Although data collection for the students has been designed to coincide with the school year, the same procedures will be followed if the data collection occurs when school is not in session.

Wave 1 data collection will commence in December 2019 with 1 school after students have begun receiving the Native Stand and Cultural Mentoring components of the intervention during the school year.

Wave 1 9- month follow-up will take place at the end of the school year in May/June 2020 as the intervention is completed. The Wave 1 12-month follow-up will take place at the beginning of the next school year in September 2020.

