**Forms:**

1.) The "Community Advisory Board Meeting Form" will be collected once per quarter after each meeting of the CAB. It will document the barriers and facilitators to intervention implementation discussed at CAB meetings, any social, environmental, political, or bureaucratic contextual factors such as the death of an elder or Tribal Council election year, that may have inhibited or facilitated intervention implementation, and any suggestions to mitigate these barriers the CAB discusses. CAB meeting notes will also be taken during each meeting.

2.) The "Whole Team Meeting Form" will document bi-monthly meetings that include [name], [name], [name], [name], the N/E outreach coordinator, the Cultural Mentor outreach coordinator, and [name]. This form will include any barriers and facilitators to intervention implementation discussed, contextual factors (social, environmental, political, or bureaucratic) discussed, suggestions, and who will be responsible for implementing these suggestions.

3.) The "Staff Training Evaluation Log" will be collected yearly and documents who has been trained, what procedures were followed during training, problems encountered during trainings, and any feedback from the trainings.

4.) The "Fidelity Reach Log and Field Notes" form includes documenting the delivery of the intervention and any field observations study staff note. It will document the date of the intervention, the length of time the intervention was delivered, specific modules delivered, and any barriers and facilitators to the delivery of the intervention.

The outreach coordinator will also document any environmental, social, political, or bureaucratic barriers or facilitators and suggested solutions to the intervention delivery. With the exception of names of staff trained, no identifying data will be collected. These files will be kept in a locked file cabinet by [name] at MSU after data collection.

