## SECTION 6: HUMAN SUBJECTS

**6.1 Institutional Review Board Approvals.** The study has approval from the Fort Peck Institutional Review Board and the Montana State University Institutional Review Board. In addition, the study has been registered with ClinicalTrials.gov. These aforementioned approvals are in agreement with the conditions for approval to conduct human subjects research as outlined in our Notice of Grant Award from the National Institute of Minority Health & Health Disparities. See Appendices for research approvals.

**5.2. Human Subjects' Characteristics.** There three groups participating in the study in which data will be collected include: 1) 15 to 18-year-old youth; 2) a parent/legal guardian; and 3) members of the Fort Peck Epi Team.

**6.3. Data Sources for Human Subjects Based on Intervention Levels.** Our study includes four levels of intervention:

**1) Individual Level.** Native Stand is a school-based, 27-module STI-, HIV-, and teen pregnancy-prevention curriculum, originally developed for rural white youth and adapted for Native youth in 2008. For our study, an adaptation of Native Stand will be implemented over 9 months in the 5 tribal high schools to educate Fort Peck tribal youth on sexual risk behavior prevention strategies by tailoring and reducing the 27 modules into 18 modules, as well as including specific community-relevant traditional and contemporary cultural lesson plans. Trained project staff will deliver Native Stand in school classroom settings during the school year as part of each school's curriculum. American Indian students only will be recruited for Levels 2 and 3 and for data collection.

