**F. Discomfort with Completing Intervention Data Collection Instruments or Disclosure Safeguards:** During the course of participation in the research, a participant may have questions concerning the data collection tools. Either the Project Director ([name]) or the Outreach Coordinator (to-be-hired) will be available at each school data collection event to answer questions. Likewise, the mentoring program Director ([name]) and her Community Mentorship Coordinator (to-be-hiredDo you want to add name?) will be available at each group mentoring meeting to answer questions. To prevent discomfort or embarrassment, the Project Director ([name]) is trained in counseling and has experience in therapeutic interaction. The PI has training and previous work experience in clinical social work and will be available to all participants via cell phone, email, or in person when she is at Fort Peck to address any concerns regarding the data collection instruments. The remaining staff will receive specialized training in sexual and reproductive health and will also be available to participants.

**G. Dissatisfaction Safeguards:** Participants will be encouraged to discuss with the PI or Fort Peck-based project personnel any possible dissatisfaction with the data collection tools or intervention activities.

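### The person who teaches Native Stand and presents Native Voices appears to help administer the follow-up surveys, which risks an upward reporting bias in condom use that the model cannot separate from the intervention effect

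*Combined protocol and SAP*

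**What the plan says.** **Delivery.** Section 2.3.4 gives Native Stand to the N/E "School Coordinator in a classroom setting as part of the students' regular class schedule". For Native Voices, the "School Coordinator will present" the sessions to students and parents. Section 6.3 is less specific: "Trained project staff will deliver Native Stand in school classroom settings during the school year", and Native Voices is implemented by a person whose name is removed.

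**Surveys.** Section 4.1 says that a named team member, "a part-time assistant, and the N/E school outreach coordinator will oversee both surveys' administration". It then lists the named person, "the assistant, and N/E's outreach coordinator" as administering the student surveys at baseline, 3 and 9 months, and the same three for the parent survey. The data collection text in Section 6 lists one named person and the outreach coordinator, with no assistant. Section 7, item 2.F, says that the Project Director or the Outreach Coordinator "will be available at each school data collection event to answer questions".

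**Outcome and safeguards.** The primary outcome is a self-reported count of condom use over the past month (student survey, items 5.5 and 5.6). The registration receipt in the appendices gives masking as none, and its H1 names 12 months for the primary analysis. Students complete the survey on tablets, in spaced groups of 20, and are told that their answers are anonymous.

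**The concern.** At baseline, whoever runs the survey has not yet taught these students. By the later follow-ups, the students may be reporting condom use in the presence of the person who taught them about condoms and refusal skills. If some students then report what they were taught, reported use rises with no change in behaviour, and it rises only in treated observations.

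The safeguards are not complete. Section 4.1 gives the outreach coordinator access to the list that links names to records, both during data collection and during delivery. Section 7 (item 3.B) has key personnel review answers for signs of risk and telephone a participant if needed. A student could reasonably think that answers can be traced, whatever the survey's introduction says.

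The parent communication outcome carries the same risk if the presenter of Native Voices also surveys the parents.

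**Working it through.** **1. Are the two titles one person?**

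| Points to one person | Points the other way |
|---|---|
| The titles are nearly identical: School Coordinator (2.3.4) and school outreach coordinator (4.1) | No section equates them |
| The outreach coordinator keeps notes on delivery: "The outreach coordinator will also document any environmental, social, political, or bureaucratic barriers or facilitators and suggested solutions to the intervention delivery" (4.2.1) | Documenting delivery is not teaching |
| The whole-team meeting list in 4.2.1 has an N/E outreach coordinator and a Cultural Mentor outreach coordinator, but no separate School Coordinator | Removed names in that list could hide one |
| | Section 6.3 has trained staff teach Native Stand and a named person implement Native Voices, while Section 7, 2.F, has the Outreach Coordinator still to be hired |

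Overlap is a strong inference, more so for Native Stand than for Native Voices. It is not a stated fact.

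**2. When does the teaching relationship exist?** Section 2.3.5 takes one baseline in all schools before any school starts. Every later student survey follows the start of that school's programme. Table 1 schedules 18 Native Stand sessions at two a month. By month 3 about 3 × 2 = 6 are done, ending with the first reproductive health session. Condoms and birth control is session 10 (10/2 = month 5), and negotiation and refusal is session 15 (15/2 = 7.5, so month 8). The concern therefore applies mainly at 9 and 12 months.

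**3. Can the model separate a reporting shift?** The second Section 3.1.5 gives Y = μ + β_j + θX_ij + u_i + e_ijl. If reported use equals true use plus a shift b that occurs only in treated observations, then Y(reported) = μ + β_j + (θ + b)X_ij + u_i + e_ijl. The coefficient on X estimates θ + b. Neither the time effect nor the school effect isolates b, and a dose coding of X does not help, because b also arises only after the programme starts.

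**4. How large could it be?** The plan's sample size reproduces: 292 × 1.3273 = 387.57, and 387.57/0.85 = 455.97, so 456. This does not test the concern, but the same paragraph (3.1.1) gives the scale: a 0.14 increase, 80% power and a 0.05 level. Taking the test as two-sided, which the plan does not state, the implied standard error is 0.14/(1.960 + 0.842) = 0.050.

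The documents give neither a baseline rate of condom use nor a misreporting rate, so both are assumed. Let p be true use and f the fraction of unprotected acts reported as protected because the instructor is present. Then b = (1 − p)f. With a true effect of zero, the rejection rate is P(|Z + b/0.050| > 1.96). For p = 0.45:

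| f | b = 0.55f | b/0.14 | b/0.050 | Rejection rate |
|---|---|---|---|---|
| 2% | 0.011 | 8% | 0.22 | 5.6% |
| 5% | 0.028 | 20% | 0.55 | 8.5% |
| 10% | 0.055 | 39% | 1.10 | 19.6% |

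Over p = 0.30 to 0.60 and the same f, b runs from 0.40 × 0.02 = 0.008 to 0.70 × 0.10 = 0.070, and the rejection rate from 5.3% to 28.8%.

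**The case against.** The strongest case against is that a reader might infer two things the documents do not establish: that the teacher and the survey administrator are certainly one person, and that the primary effect is therefore biased upward.

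- **Identity.** It rests on similar titles and a staff list with names removed. This stands, and the point has to be put as an apparent overlap.
- **Who is in the room.** The coordinator is one of up to three administrators and also helps at baseline. Only the teaching relationship is new after baseline. This stands.
- **The primary time point.** The sentence that names student survey administrators covers baseline, 3 and 9 months. Twelve months is reached through the general statement that "the N/E school outreach coordinator will oversee both surveys' administration", and through wording that carries the procedure over to graduates and to surveys outside term. For Wave 1 that survey falls in September 2020, after delivery ends in May or June. The link is weaker here, but the plan names no one else for it.
- **Size.** Tablets, spacing and the anonymity statement reduce pressure. At f = 2% the false-positive rate hardly moves. Having been taught can shift answers whoever runs the survey, so removing the instructor removes only part of any shift. All of this stands.
- **Practicality.** A ban on attendance at every time point would conflict with the coordinator's part in assent and consent review, and with the availability rule in Section 7, 2.F. This stands too, and it limits what should be asked for.

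None of this answers the main point. The text supplied does not separate delivery from outcome collection, and it describes no objective check of the outcome and no measure of social desirability.

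**Conclusion.** The concern holds as a risk of upward reporting bias, mainly at 9 and 12 months, and not as an established bias. It depends on the two coordinator titles being one person, which is likely but unstated, and on some students answering differently before their instructor. Upward is the plausible direction. The size is unknown: the range of 0.008 to 0.070 follows wholly from assumed values of p and f. The rejection rates also take the standard error from the plan's own power claim. A larger real standard error would lower them but would leave the shift in the estimate as it is.

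The change should be made before follow-up surveys begin, because the planned model cannot remove the shift afterwards. If different people hold the two roles and the survey staff lead no sessions, a sentence saying so settles most of the point.

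**What to change.** State in 2.3.4 and 4.1 that anyone who leads Native Stand, Native Voices or mentoring sessions at a school does not administer, or stay in the room during, that school's 3-, 9- and 12-month student surveys or 9- and 12-month parent surveys. Use the survey staff already listed, the named team member and the part-time assistant, to the extent that they lead no sessions. Preferably the same staff also run the baseline survey itself, so that the administrator does not change with treatment.

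The coordinator can still review assent and consent, and be on call outside the room. The Project Director can meet the availability rule in Section 7, 2.F, and if that person leads sessions, can do so from outside the room.

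State whether one person holds the two coordinator roles and who runs the 12-month survey. Reconcile 2.3.4, 4.1, the delivery and data collection text in Section 6, and Section 7, 2.F.

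The cost is wording and some rescheduling, with one fewer adult per group of 20. Section 6 lists no assistant, so the plan should confirm that enough staff who lead no sessions are available. The change does not remove any shift that comes from having been taught.
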